#### 1 Review Type (Choose one)

Please choose which level of review best fits your research. This is an investigator's assessment of review and does not preclude the IRB from alternate determinations. In cases where the investigator and the IRB's determination of review conflict, the IRB's determination will be considered the official determination.

**Note**: Expedited review does not refer to the timeliness of the review of your protocol, but specific categories of research defined by OHRP. If you would like help determining which type of review best fits your research study, please contact the IRB staff in the Office of Research Support & Compliance: https://research.utexas.edu/ors/human-subjects/get-help/

- a □ Full Board Review Greater than Minimal Risk Research
- **b ⊠** Expedited Review Minimal Risk Research

## **2** Research Hypotheses

Please describe the research aims and hypotheses in the box below. To input text, click in the box below and start typing.

Note: Procedures will be explained in a separate section below.

The purpose of the proposed study is to preliminarily evaluate a technology-based information and coaching/support program, TACAD (Technology-based Information and Coaching/Support Program for Asian American women who are family caregivers of persons living with Alzheimer's Disease), in improving health outcomes of Asian American women who are family caregivers of persons living with Alzheimer's disease (AACA) and their care recipients. The **specific aims** of the study are to:

- Aim 1. Qualitatively evaluate TACAD through an expert review and a usability test.
- **Aim 2**. Quantitatively evaluate the preliminary efficacy of TACAD in improving health outcomes of AACA and their care recipients.
- -Hypothesis 1. After controlling for background and health/disease factors, the intervention group (AACA who use TACAD and the Alzheimer's Association [AA] website) will show significantly greater improvements than the

active control group (AACA who use only the AA website) in their health outcomes (stress, physical and psychological symptoms, and quality of life) and their care recipients' health outcomes (activities of daily living, behavioral and psychological symptoms, mood status, and quality of life) from baseline (pre-test) to Time Points 1 (post 1 month) and 2 (post 3 months).

- -Hypothesis 2. After controlling for background and health/disease factors, the intervention group will show significantly greater improvements than the control group in caregiving experience (caregiving activity, coping, caregiving competence, and caregiving skills) from baseline to Time Points 1 and 2.
- -Hypothesis 3. After controlling for background and health/disease factors, the intervention group will show significantly greater improvements than the control group in theory-based variables (attitudes, self-efficacy, perceived barriers, and social influences related to caregiving of PLAD) from baseline to Time Points 1 and 2.

#### 3 Study Background

Provide the rationale and the scientific or scholarly background for the proposed activity, based on existing literature (or clinical knowledge). Describe the gaps in current knowledge that the project is intended to address.

PLAD spend most of the course of their illness in the community and receive most of their care from informal (usually family) caregivers. Currently, about 15 million adults, mainly women, annually provide 17.9 billion hours of family care for community-dwelling persons living with Alzheimer's and other illnesses. The situation is worse for **AACA**. Under-detection of cognitive impairment among Asian Americans remains prevalent, and their cultural stigma produces suboptimal dementia management, placing them at a greater risk than Whites. Although Asian Americans include highly diverse sub-groups, all Asian Americans across the sub-groups share many common characteristics, one of which is "filial piety," the belief that family members are in charge of caregiving roles. Mainly due to this cultural belief, 42 percent of Asian Americans reportedly provide care to an older adult while 22 percent of the general population provides care to an older adult.

The negative influences of caregiving on health outcomes of family caregivers are well documented. 8-10 The chronic stress of their role places them at greater risk for morbidity and mortality than non-caregiving peers. 8-10 The adverse effects on their psychological and physical well-being are extensive. 10-14 Furthermore, racial/ethnic minority women are more likely to suffer from caregiving burden compared with their counterparts, mainly due to their cultural attitudes related to AD and caregiving. 15-17 Furthermore, they rarely complain about their caregiving burden, delay seeking help, and seldom get support due to their cultural values, beliefs, and language barriers. 4-6,17 Subsequently, they have lower quality of life and fewer sources of information and support than Whites. 4-6,17 To reduce the burden of caregiving on health outcomes among family caregivers of PLAD and subsequently improve health outcomes of care recipients, many psychoeducation interventions were developed and used to provide information and support/coaching. Indeed, a number of psychoeducation programs for caregivers have been developed and tested in relieving distress, increasing self-efficacy, managing caregiving challenges, and enabling caregivers to sustain care over longer periods of time. 19-22

As mentioned above, however, **existing psychoeducational interventions** have rarely succeeded in achieving their goals among racial/ethnic minorities including Asian Americans because of several reasons.  Again, one major reason is the lack of consideration on caregivers' cultural attitudes related to AD and caregiving.  For instance, due to cultural hesitance to discuss dementia,  Asian Americans tend not to share their caregiving experience (e.g., heavy burden of caring, psychological and physical symptoms) until they get severe/serious problems that cannot be tolerated anymore. These women consequently shoulder the heavy burden of caregiving without adequate support although there exist some information and/or coaching/support available to them.  However, there is virtually no program that considers these women's cultural attitudes. Also, another major reason is: many caregivers cannot take part in existing programs because most require them to arrange care for the care recipients while they attend the programs. 

**Technology-based programs** could help overcome these two major drawbacks of existing programs by incorporating cultural tailoring and providing 24-hour access through the Internet without physical transportation. Also, in a meta-analysis of randomized clinical trials, Davies et al. found that technology-based programs were effective in producing changes in health outcomes. Researchers also supported the effectiveness of technology-based interventions in approaching marginalized people with stigmatized conditions (e.g., racial/ethnic minorities). These marginalized groups report greater interest in e-health than their more affluent counterparts. Moreover, Internet use by Asians is greater than that of any other racial/ethnic groups; about 97% of Asian Americans have access to the Internet. The PSs, Asians preferred a technology-based program that would not require travel to a location outside of their home. About 94% of Asian-American households own a cell phone (compared with 86% of total population). About 94% of Asian-American households own a cell phone (compared with 86% of total population). About 94% of Asian-American households own a cell phone (compared with 86% of total population).

Despite the reported strengths, few technology-based interventions are actually available for MWPLAD. A meta-analysis of 12 interventions using information and communication technologies among informal caregivers of persons living with dementia identified only two computer-based studies. These two studies reported significant positive effects of the computer-based interventions that included educational modules and videos, decision support, and communication features. Kajiyama reported a significant positive effect on caregivers' stress (p=.017), and Brennan indicated significant improvement in caregivers' decision-making confidence (p<.01). However, none of these programs specifically targets or offers features most appealing to AACA.

TACAD that will be tested in the proposed study offers several unique features that were rarely used in existing programs. First, none incorporated racial/ethnic minorities' cultural attitudes in the design, and none used cultural tailoring. Yet, cultural tailoring is essential in providing effective information and coaching/support for Asian American caregivers. For example, Confucian cultural heritages prescribe Chinese women to live in harmonious social relations, subsequently inhibiting them from expressing potentially disruptive and distressing emotions and/or symptoms. Thus, technology-based programs that do not consider this cultural attitude would not best serve this group. It is also well known that the programs culturally tailored to meet the specific needs of a subgroup would be much more effective than generic programs because tailored programs address only those factors known to be important to specific recipients. 61-64 TACAD has multiple components that are culturally tailored to AACA based on the findings from PSs and the criteria for rigor in cross-cultural research (see Intervention). Second, the self-adaptation functionality included in TACAD allows further personalization of the intervention components using a machine-learning method (Genetic Algorithm; see the section on TACAD), which was never used in existing programs. Through this functionality, TACAD can deliver the most relevant and effective information and coaching/support to each participant while considering diversities among AACA. Because there exist diversities even among the two sub-ethnic groups of Asian Americans,  this personalization is necessary for AACA. Furthermore, this is consistent with the NIH's direction related to precision/personalized medicine/health. Third, none of the programs incorporated both group and individual (real-time and personalized) coaching/support by culturally matched bilingual healthcare providers. There exist added benefits to protocols that include both group and individual coaching/support. Group coaching/support through non-faceto-face interactions work well for Asian Americans because of their collectivist culture.70-72 Also, individual (realtime and personalized) coaching/support through non-face-to-face interactions would work well for those whose cultures still stigmatize dementia. 73-76 Furthermore, culturally matched bilingual interventionists can ensure efficacy in coaching/support, limit the potential for harmful communications, provide reliable and objective information/resources, and nurture a positive group culture in culturally appropriate and sensitive ways. Fourth, peer-based social media services that allow individuals to generate public profiles, develop a list of users with whom to share connections, and interact with the users through Internet interactions and instant messaging are rarely used in existing programs.80 Social media sites such as Facebook effectively communicate and encourage user participation around health topics. While social media as a health tool is understudied, findings indicate its effectiveness in providing information and coaching/support to racial/ethnic minorities.81-83 Finally, few existing programs incorporate VR technology in the intervention. VR can be a more accessible, scalable, and appealing delivery method for this specific population since they would not need to travel. VR can be used to create highly ecologically controlled simulations resembling the daily life contexts in which patients' daily instrumental activities usually take place. The immersive and engaging virtual environment promotes caregivers' actual understanding of PLAD' daily experience and provides a sense of control and multiple dimensions of empathy. Actually, VR has been widely used to help family members learn more about the challenges their loved ones with dementia face, and to build empathy among family caregivers of PLAD. This effectiveness in increasing empathy has been reported in the literature, and VR was reported to be an effective intervention to train caregivers of persons with dementia. Acad originally, TACAD includes a VR component based on "A Walk Though Dementia" (a free Android & iOS Virtual Reality app giving an insight into life with dementia), which will be used to change AACA's attitudes related to AD and caregiving by increasing their empathy. However, the original VR that we planned to use was discontinued by the developer and only a 360 degree video clipping of the VR component is currently available. Thus, the VR component was replaced with the 360 degree video clipping of the VR. In summary, if TACAD, by incorporating all these components, proves to be effective, it can fill the gap in these programs and ultimately reduce health disparities in racial/ethnic minority caregivers of PLAD. This study will also accelerate the translation of the technology-based programs into various settings and populations and will be an important contribution to health and quality of life among racial/ethnic minority caregivers of PLAD.

## 4 Design and Methodology

Provide a brief description of the study design or data collection methodologies. Details regarding protocol specific research procedures will be discussed in a later section.

The study includes two phases: (a) a usability test and an expert review (Phase 1) and (b) a pilot randomized clinical trial (Phase 2). Phase 1 has been completed at Emory, and only Phase 2 will be conducted at Univ. of Texas at Austin (UT Austin). For Phase 2, the data will be collected at three points: (a) pre-test; (b) post 1 month; and (c) post 3 months. The collected data will be analyzed after the data collection of all the participants is completed.

## 5 Data Analysis

Describe the data analysis plan, including any statistical procedures or power analysis.

The data will be randomly assigned with serial ID numbers. All tests will be assumed two-sided and an alpha level of .05 will be used. SAS 9.4 will be used for data processing and all statistical analyses. Missing data will be handled by multiple imputations of dependent values. 101–103 Analyses just of complete data will be conducted and comparisons of groups with and without missing data will be made. In addition, sensitivity analyses of complete data will be conducted and compared imputed data analysis. An **intent-to-treat** analysis will be employed. For **Hypotheses 1 to 3**, differences in continuous outcome measures over time will be examined using **linear mixed-effects modeling.** In particular, we will fit mixed effects models to each continuous outcome measure. We will use random intercepts as well as explore random slopes to represent subject level variability. Fixed-effects corresponding to group, time and group x time interaction will be included in the model. A significant group x time interaction will indicate substantial differences in the groups over time. Restricted maximum likelihood method will be used for estimation, and the most appropriate covariance structure will be examined.

Since Data and Safety Monitoring Boards (DSMBs) are required only for phase III clinical trials (NOT-OD-00-038.html), we do not include a DSMB for this intervention study. For the proposed intervention study, we have

the following data safety monitoring plan (DSMP). First, to manage and protect the data collected, only summary data will be openly accessible to funding agency or will appear in publications. Research participants will be informed that they are free to decline to answer any questions they do not wish to answer or to stop participating in the project at any time. When a participant withdraws from participation, the data that they have provided will be immediately removed. Also, the data will have no identifying information to link a subject to the data.

The participants' records will be handled as confidentially as possible. Only the research team will have access to the study records. As mentioned above, only a serial ID number assigned by the researcher will be attached to the data, and the data will be stored in a locked file cabinet in a research office. No identity information, including IP addresses, will be attached to any of the individual or group data. Therefore, research participants will not be identifiable directly or through the identifying information linked to subjects. No individual identities will be used in any reports or publications that will result from this study. Additionally, as explained above, the Web site will be developed and maintained such that it conforms to the HIPAA standards. Finally, data in the servers will be daily monitored by [name] to ensure its safety and security.

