months. Only the intervention group will use TACAD for **3 months**. Basically, they need to use TACAD and/or the AA website whenever they want to use; no requirement for reimbursement. They are recommended to visit the project website at least once a week and the intervention group is recommended to have weekly coaching/support sessions with the interventionists through chatting. At first time of use, the participants will have an informational session on the proper use of AA website and TACAD (with instructions on headsets) by phone and/or a webcam. During the intervention, the participants will provide their feedback on the research process as well as TACAD. Two weeks before the end of the 1st and the 3rd months, both groups will fill out the next set of the instruments; it usually takes about 30 minutes to complete each questionnaire. The questionnaires will be provided via **Qualtrics**. In addition, during the intervention period, the participants will be screened using the PHQ-9 only if the research team identifies severe depressive symptoms or suicidal ideation at any time point. We will make immediate recommendations for psychiatric referral for those with scores more than 10 on the PHQ-9 (the cut-point of moderate depressive symptoms; range=0~27) as the literature suggestsIn such cases, participants will also be dismissed from the study.

TACAD. TACAD has four components in three languages (English, Mandarin Chinese, and Korean): (a) 2 sub-ethnic specific social media sites; (b) interactive online educational modules; (c) online resources; and (d) a 360 degree video clipping (a replacement of the VR component that was originally planned). The original VR that we planned to use was discontinued by the developer and only a 360 degree video clipping of the VR component is currently available. Thus, the VR component was replaced with the 360 degree video clipping of the VR. Two languages other than English were adopted because they are the primary languages of Chinese Americans or Korean Americans. The comparability of different language versions has been ensured through the standard-back

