translation process. The social media sites will be assisted, coached/moderated, and monitored by culturally matched bilingual RNs under the supervision by PIs. Coaching/support through social mediate sites (with chat functions) will focus on: (a) changing attitudes toward and beliefs about AD and caregiving, (b) building selfefficacy for caregiving, (c) minimizing information needs and uncertainty, and (d) enhancing social support through multiple ways. Within the project website, a social media site (like Facebook) is included. The site is developed by [name] and owned by him. The participants' activities are daily monitored by the interventionists and [name] to prevent any possible harmful effects. The RNs will be trained by the PI. Her/his first 10 messages through social media sites and chat functions will be monitored/evaluated by the research team, and the team's feedback will be incorporated into her/his subsequent interactions. The social media site will be very similar to Facebook. All participants can post their messages (e.g., sharing their experience) and pictures and they can see others' postings. The participants will use their pseudonyms that they choose when they join the study, but their profile pictures will not be posted. All postings will be visible only at the project website. No identifiers will be used except pseudonyms. We also developed online educational modules while considering the women's cultural attitudes found in the literature: TACAD aims to correct misinformation on AD and caregiving by providing stateof-science evidence-based educational content and to provide examples of culturally appropriate caregiving strategies that can be easily adopted. Culturally relevant content (e.g., filial piety, respect for elderly, mind-body interactions, etc.) and culturally tailored educational materials and online resources from Asian scientific authorities are also incorporated. Again, 360 degree video clipping components based on "A Walk Through Dementia (WTD)" will be used to help caregivers learn more about the challenges their loved ones with dementia face, and to build empathy among the caregivers (subsequently changing their attitudes). WTD uses VR technology to give an idea of the challenges faced by people with dementia. Using 3 everyday scenarios (at the supermarket, on the road and at home), users are given insight into some of the symptoms that people with different forms of dementia including AD may experience. The original VR that we planned to use was discontinued by the developer and only 360 degree video clippings of the VR component is currently available. Thus, the VR component was replaced with the 360 degree video clippings of the VR. The 360 degree video clippings basically have the same content of the VR component without the 3-dimentionality, which could be just viewed through Youtube site without any device. They are:

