For instance, the webpage on caregiving includes information on caregiving, care option, financial/legal planning, caregiver health, daily care, stages and behaviors, and safety. The content will be available in the three languages at the project website. The usages of the AA website and additional information searches (the participants will use them only through the project website) will be automatically recorded through the project server and later used for data analyses. Both groups will be asked to maintain their usual care. The interventionists will weekly remind the control group to use the AA website.

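### TACAD women share peer sites and nurse coaches and controls do not; the section 5 model has only subject-level random effects, so its standard errors are too small if outcome changes correlate within site or coach

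*Combined protocol and SAP*

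**What the plan says.** Women are randomized individually within sub-ethnic group (Phase 2 (Aim 2); section 17). What follows differs by arm. The plan says "Only the intervention group will use TACAD for" three months, and TACAD includes "2 sub-ethnic specific social media sites". On staffing: "The social media sites will be assisted, coached/moderated, and monitored by culturally matched bilingual RNs under the supervision by PIs". On peer contact: "All participants can post their messages (e.g., sharing their experience) and pictures and they can see others' postings". In addition, "the intervention group is recommended to have weekly coaching/support sessions with the interventionists through chatting". The only interventionist contact described specifically for controls is a prompt: "The interventionists will weekly remind the control group to use the AA website".

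Section 5 fits a linear mixed model to each continuous outcome with fixed effects for group, time and their interaction, tested two-sided at .05. On random effects it says "We will use random intercepts as well as explore random slopes to represent subject level variability". It leaves the covariance structure to be examined. Neither section 5 nor section 15 (sample size rationale) mentions site, coach, an ICC, a design effect or a cluster-robust variance.

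**The concern.** Grouping arises after randomization and in one arm only. Women on the same site read each other's posts, and women with the same nurse receive that nurse's style and skill. Such sharing is part of the intended mechanism: section 3 promotes group as well as individual coaching, and Hypothesis 3 counts social influences among its outcomes. Outcomes of women in the same group may therefore move together.

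The planned model lets measurements correlate within a woman over time but treats the 60 women as independent. If there is positive correlation between women, the variance of the TACAD mean change is understated, intervals are too narrow, and a strong or weak nurse or peer group is credited to the program as if 30 independent women had shown it. Section 5 takes a significant interaction as evidence that the groups differ, so the standard error of that contrast carries the conclusion.

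**Working it through.** **Inputs from the documents.** 30 women per arm (section 15); two sites, one per sub-ethnic group, in the TACAD arm (Phase 2 (Aim 2)); two-sided alpha .05 and subject-level random effects only (section 5).

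**Inputs assumed.** An equal split of TACAD women, 30/2 = 15 per site; alternatively four coaches with 30/4 = 7.5 women each; ICC of change from baseline between 0 and 0.10. The ICC of change is the relevant one because the test is on group by time.

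**The plan's own figure.** Section 15 gives 105 per group for a difference of 0.5 (read as 0.5 SD, since no SD is stated), 80% power and alpha 0.00625. The normal approximation gives 2 × (2.734 + 0.842)² / 0.5² = 102.3, so 103 per group. The exact two-sample t calculation gives 105 (power 0.804). Both treat participants as independent, so the figure contains no allowance for clustering.

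**Formulas.** With clustering in the TACAD arm only, equal arms and equal variances:
- Design effect in the TACAD arm: DE = 1 + (m − 1) × ICC
- True over reported standard error of the arm difference: R = sqrt((DE + 1)/2)
- Type I error of a nominal 5% test: 2 × (1 − Φ(1.96/R))

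Example, m = 15 and ICC 0.05: DE = 1 + 14 × 0.05 = 1.70; R = sqrt(2.70/2) = 1.162; 1.96/1.162 = 1.687; type I error 9.2%.

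| Assumed cluster | ICC | DE | R | Type I error |
|---|---|---|---|---|
| Site, m = 15 | 0 | 1.00 | 1.00 | 5.0% |
| Site, m = 15 | 0.01 | 1.14 | 1.03 | 5.8% |
| Site, m = 15 | 0.05 | 1.70 | 1.16 | 9.2% |
| Site, m = 15 | 0.10 | 2.40 | 1.30 | 13.3% |
| Coach, m = 7.5 | 0.01 | 1.065 | 1.02 | 5.4% |
| Coach, m = 7.5 | 0.05 | 1.325 | 1.08 | 6.9% |
| Coach, m = 7.5 | 0.10 | 1.65 | 1.15 | 8.9% |

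In the site case, the 30 TACAD women carry the information of 30/1.70 = 17.6 independent women at ICC 0.05.

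**Simulation check, two sites of 15.** A two-group test on change (40,000 runs) rejected in 4.9%, 5.9%, 9.4% and 13.1% of runs at ICC 0, 0.01, 0.05 and 0.10. A three-wave random-intercept group-by-time F test (20,000 runs; total variance 1 and within-woman correlation 0.5 before a cluster variance of 0, 0.01, 0.05 or 0.10 was added at follow-up) rejected in 5.0%, 5.9%, 8.8% and 13.1%. The formula is adequate for this purpose.

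**The case against.** **No ICC is given.** At zero there is no bias, and at 0.01 it is minor. A reader might infer that the reported standard errors will be too small and the error rate above 5%. The documents do not support that: they describe shared exposure, not its correlation. This stands, and the point is conditional.

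**The coaching structure is unknown.** A reader might also infer that a handful of nurses coach everyone. The plan gives no number, caseload or allocation. The 15-per-site split is likewise assumed. Use of the program is voluntary, and much of it is individual (modules, resources, videos, one-to-one chat), so shared exposure may be uneven. Smaller coach-level clusters give less inflation. This also stands.

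**Site can be regarded as a fixed factor.** Site coincides with sub-ethnicity, the randomization stratum, and the inclusion criteria admit only Chinese and Korean women. A site effect confined to TACAD is then a group-by-sub-ethnicity interaction, which fixed terms can absorb. That is right for the site component and belongs in the remedy. It does not deal with correlation through coaches within a site. A sub-ethnicity main effect alone would remove only differences common to both arms.

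**The plan may cover this elsewhere.** The open choice of covariance structure most naturally concerns repeated measures within a woman. The crosstalk check under Phase 2 (Aim 2) concerns contamination of the comparison, not correlation within the TACAD arm. Neither answers the point.

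**It is a pilot.** Section 15 calls the study explorative, and section 2 aims at preliminary efficacy. That limits the stakes and argues for a light remedy, but section 5 still tests at .05.

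**Conclusion.** The point holds in conditional form. The TACAD arm is partially nested, and nothing in the analysis plan or sample size allows for it. If changes correlate positively within site or coach, the group-by-time standard errors are understated. For ICC 0 to 0.10 the factor runs from 1.00 to 1.30 with two sites of 15 (type I error 5.0% to 13.3%), and from 1.00 to 1.15 with four coaches of 7.5 (5.0% to 8.9%). These ranges rest on assumed cluster sizes and ICCs; none is a prediction for this trial. It would also be too strong to require a result to survive the whole range before it is called robust, because nothing in the documents fixes that range as a decision rule. A prespecified sensitivity analysis beside the unchanged primary model is proportionate.

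**What to change.** Record which RN coaches each TACAD woman, during delivery, because this may be hard to reconstruct later. Site follows from sub-ethnicity, which is already collected.

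In section 5, keep the primary model and add a prespecified sensitivity analysis:

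- (a) Include sub-ethnicity and its interactions with group and time as fixed effects, and show estimates by sub-ethnic group (site).
- (b) If enough coaches deliver TACAD, fit a coach random effect in the TACAD arm only.
- (c) Otherwise, report the arm contrasts in change from baseline with the standard error multiplied by sqrt((DE + 1)/2), where DE = 1 + (m − 1) × ICC, for ICC 0, 0.01, 0.05 and 0.10, with m set to the actual site or coach cluster size.

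State that two sites cannot support estimation of the ICC, so the values in (c) are assumed.

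The cost is one extra recorded variable, one table and wider intervals in the sensitivity analysis.
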